2.3 ENDPOINTS

2.3.1 Primary Endpoint/Outcome

Physical Component Score (PCS) of the SF-36 HRQoL questionnaire at 90 days post-randomisation.

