2.3.2 Secondary Endpoints/Outcomes

Patient centred outcomes:

- 1. Physical Component Score (PCS) of the SF-36 HRQoL questionnaire (and its four sub-domains) at 30 and 90 days post-randomisation.
- 2. Patient fatigue (Fatigue Severity Scale (FSS)) at 30, 90 and 180 days post-randomisation
- 3. Mental component score SF-36 (and its four sub-domains) at 30, 90 and 180 days post-randomisation.
- 4. Activities of Daily Living (ADLs) (WHODAS questionnaire⁴) at 90 days post-randomisation
- 5. Patients alive at 30, 90 and 180 days post-randomisation
- 6. Patients alive at 5 years post-randomisation derived from data linkage
- 7. Haemoglobin concentration at 30 days post-randomisation

Resource use and cost-effectiveness (based on data linkage and questionnaires):

- 8. Post-ICU length of hospital stay;
- 9. Care costs during 180 days post-randomisation.

- 10. Incremental cost per QALY at 180 days
- 11. Care costs derived from data linkage during 5 years post-randomisation (depending on results from shorter term outcome analysis)

Process and Safety outcomes:

- 12. Protocol compliance (during intervention index hospital stay)
- 13. Hb concentration (during index hospital stay)
- 14. RBC use (during 90 days follow up)
- 15. New Infections (during 90 days follow-up)
- 16. Transfusion-related adverse events (during 90 days follow-up)
- 17. Major adverse cardiovascular events (MACE; during 90 days follow-up)

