5.2.3 Withdrawal of Study Participants

There will be no pre-defined participant withdrawal criteria based on medical criteria. Participants are free to withdraw from the study at any point or a participant can be withdrawn by the Investigator if this is considered clinically appropriate. In the case of incapacity, the representative of the participant can also withdraw the patient from the trial.

It is recognised that responsible clinicians may decide to suspend group allocation in certain circumstances based on their clinical judgement. Examples may include bleeding events, acute cardiovascular events, or other periods of clinical deterioration. In this situation, the patient should not be withdrawn from the trial unless the clinician specifically requests this. Ideally, the patient should be re-established on group allocation after the acute situation has resolved. Wherever possible the patient should remain in the trial for follow-up even if a decision is made to permanently suspend group allocation (see option 1 below).

If withdrawal occurs, the participant will have the following withdrawal options:

- 1. From any further study intervention only (ie the two transfusion groups). Further blood transfusions at the discretion of the clinical team. However, all follow up data collection (including the visit at 30 days if appropriate) will be completed as far as possible. The priority in this situation is the completion of the primary outcome (SF-36 PCS at 90 days).
- 2. From any further study intervention and data collection. All data collected until the point of withdrawal can be retained. In this situation, effort should be made to request that the primary outcome data at 90 days (SF-36 PCS) can be collected even if other

follow up is not completed. If the participant agrees, then this is re-classified as 'option 1' but restricted to primary outcome.

3. From all aspects of the trial and follow up. All research data collected to be removed from analysis.

If withdrawal occurs, the primary reason for withdrawal will be documented in the participant's case report form, if possible. The type of follow-up (if any) will be documented in the case report form.

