6.2 LONG TERM FOLLOW UP ASSESSMENTS

Following randomisation, assessment will be carried out at the following time points (see also table 1) irrespective of whether the patient remains in the acute hospital (intervention still ongoing) or has been discharged from the acute hospital (intervention period completed).

For all follow up visits, vital status should be confirmed and telephone contact made at the start of the visit window to alert the participant to the follow up and arrange a suitable time and method. To promote completeness the Physical Component Score (PCS) of the SF-36 should be done at this initial telephone contact wherever possible, especially at 90 day follow up.

If a participant opts for postal or online follow up, the local research team should check 7 days after the visit window opens that questionnaires have been completed. If questionnaires are not complete, the research team should contact the participant and offer to complete via the telephone or online with assistance given over the phone if required. A second telephone call should be undertaken to remind the participant if the first telephone call does not result in the participant returning the questionnaire.

30 day follow up (7 days prior or 14 days post visit date for all aspects of the follow-up visit). Ideally this visit will be conducted in person to allow blood sample collection. Arrange this visit with the participant before discharge if possible. In the event the participant declines blood sample, conduct visit remotely using the methods below.

- Vital status* and follow up to be carried out by the local research team.
- Follow up questionnaires
- o Data collection
- Blood sampling

90 day follow up (+/- 14 days) - prioritise primary outcome

- Vital status* will be checked and confirmed by the local research team. Follow up questionnaires will be undertaken by the local research team (or delegated individual).
 - Completion order as follows to ensure primary outcome is collected:
 - 1. Physical Component Score (PCS) of the SF-36
 - 2. Mental Component Score (MCS) of the SF-36
 - 3. Fatigue Severity Scale (FSS)
 - 4. WHODAS ADLs questionnaire
 - 5. Health Service Utilisation

Participants should be offered several ways in which to complete and return the follow up questionnaires:

- 1. **Telephone call** the participant can complete with the aid of a member of the trial team. *This is the preferred method.*

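### The SF-36 PCS is handled as a block that can be collected alone, so a contact that stops after it may not give a scoreable primary outcome

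*Protocol*

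**What the plan says.** Section 2.3.1 sets the primary outcome as "Physical Component Score (PCS) of the SF-36 HRQoL questionnaire at 90 days post-randomisation". Section 2.3.2 gives the PCS four sub-domains of its own and lists the mental score in parallel: "Mental component score SF-36 (and its four sub-domains) at 30, 90 and 180 days post-randomisation".

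Three operational instructions follow that division.

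- **First call (section 6.2, all follow-up visits).** "To promote completeness the Physical Component Score (PCS) of the SF-36 should be done at this initial telephone contact wherever possible", with particular stress on day 90. The rest of the SF-36 is not named.
- **Completion order (section 6.2, day 90).** The list is introduced by "Completion order as follows to ensure primary outcome is collected". Step 1 is the PCS; the next line is "2. Mental Component Score (MCS) of the SF-36"; FSS, WHODAS and health service utilisation come after. Day 180 has the same order without WHODAS. Table 1 also lists PCS and MCS as separate measurements.
- **Withdrawal option 2 (section 5.2.3).** "effort should be made to request that the primary outcome data at 90 days (SF-36 PCS) can be collected", even where nothing else is. The section adds: "If the participant agrees, then this is re-classified as 'option 1' but restricted to primary outcome".

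Section 9.1 places the PCS on a scale with a normal population average of 50. The protocol does not say how the PCS is scored, which items make up the PCS step, or how a half-completed SF-36 is handled.

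**The concern.** PCS and MCS are two summary scores from one questionnaire, not two questionnaires. Under the usual norm-based scoring (assumed here, because the protocol does not state it), each summary score weights all eight domains, the mental ones included. The smallest set of items that gives a standard PCS is then the whole SF-36. An instruction to secure the PCS first, or only the PCS, would protect too small a unit.

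The patients exposed are those who break off between steps 1 and 2, those who answer only the PCS part at the first call and never complete the rest, and those on the restricted withdrawal route. For them the choice would be a missing primary outcome or a score built from the physical domains alone. The second option puts a different measure into the same analysis, and the 5-point difference and SD of 12 in section 9.1 need not carry over to it. Section 9.2.1 derives SF-6D utilities from the same questionnaire, so partial forms may also weaken the QALY analysis.

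An analysis plan can choose a scoring rule, but it cannot recover items that were never asked.

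**Working it through.** **1. Reproduce the plan's figures (section 9.1).** Inputs: difference 5, SD 12, two-sided 0.05, power 90%, allocation 1:1.

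- Per arm: 2 × (1.960 + 1.282)² × 12² / 5² = 121.05, rounded up to 122; total 244, as stated.
- 20% loss: 244 / 0.80 = 305, as stated.
- 30% loss: 244 / 0.70 = 348.6, so 349 against the stated 346. Since 346 × 0.70 = 242, the gap is immaterial here.

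**2. Number of responders.** Section 9.1 reports 75% completion of the primary outcome in May 2024. Read as a share of all randomised, 346 × 0.75 = 259.5, about 260.

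**3. Loss if some stop after the physical items.** The share who stop is not in the protocol; 2-5% is an assumption.

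- 2%: 0.02 × 260 = 5 lost, 255 left.
- 5%: 0.05 × 260 = 13 lost, 247 left.

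**4. Power.** Two-sample t-test, noncentrality (5/12) × √(N/4), N − 2 degrees of freedom.

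| Evaluable N | Noncentrality | Power |
|---|---|---|
| 244 (plan's target) | 3.25 | 90.0% |
| 260 (no loss) | 3.36 | 91.7% |
| 255 (2% lost) | 3.33 | 91.2% |
| 247 (5% lost) | 3.27 | 90.3% |

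On this base the worst assumed case still leaves more than the 244 required.

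**5. Sensitivity to the base.** If the 75% refers to survivors only, the reported 12/182 deaths give 346 × (170/182) × 0.75 = 242. That is the same starting point as the planned 30% loss. Taking 5% from 242 leaves 230, and power goes from 90.0% to 88.5% (normal approximation). The change is again about 1.5 percentage points. It may also count the same patients twice, because an unscoreable form is one of the losses that a completion rate or loss allowance can already contain.

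**6. Which instructions change what is collected.** At days 90 and 180 the MCS step directly follows the PCS step, so a patient who finishes both gives a complete SF-36. The wording matters at the first call, at a break between the two steps, and on withdrawal option 2.

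**The case against.** The strongest reply is that the decisive step is not in the protocol. No scoring algorithm is stated, a population mean of 50 fits norm-based scoring without fixing the weights, and other algorithms score physical health from the physical scales alone or estimate missing scales. Scoring rules are commonly left to the analysis plan, and section 9.2 defers statistical detail there. This stands, and it makes the point conditional. A reader might infer that patients who stop after step 1 will certainly have no primary outcome; the protocol does not support that.

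It is also true that the SF-36 as a whole already precedes the other questionnaires, and that section 7.2 and the summary treat it as one instrument. Section 6.2 has sites check postal and online returns, offer help by telephone and make a second call, so a first call limited to the PCS need not be the last contact. The withdrawal text could be read as whatever items the PCS needs. These safeguards make the affected group small. They do not remove it, because the first-call and withdrawal instructions name the PCS alone and staff are not told that more is required.

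A reader might also infer a power shortfall by taking 13 lost outcomes from the target of 244, which gives 231 and 88.4%. That mixes two bases: the 13 is 5% of 260 responders, and 260 − 13 = 247.

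Finally, one might infer that the frailest patients are the ones who stop. Section 1.1.1 describes fatigue as common and often severe, which makes selective loss plausible, but nothing in the protocol shows who stops between the two steps.

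**Conclusion.** The point holds as a conditional weakness in the collection instructions. Sections 5.2.3 and 6.2 rely on the PCS alone to secure the primary outcome; under standard eight-domain scoring that may not be enough to compute it. A loss of primary outcomes has not been shown.

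On 75% of 346 responders and an assumed 2-5% stopping after the physical items, 5-13 outcomes would be lost and power would move from about 91.7% to no lower than about 90.3%. The result rests on three assumptions: norm-based scoring over all eight domains, the 2-5% share, and 75% being a proportion of those randomised.

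The case for acting is that the missing data would be avoidable, could be selective in an unblinded trial where completion was already only 75%, and could tempt the analysis into mixing two versions of the primary outcome. The change is essential under eight-domain scoring and harmless under any other.

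**What to change.** In section 5.2.3 (option 2), in section 6.2 (first telephone contact, and the 90-day and 180-day completion orders) and in Table 1, replace the separate PCS and MCS steps with: *SF-36, all items, completed first, in one contact where possible*. The remaining questionnaires follow in their present order. Send sites a one-line memo now, since items not asked at day 90 cannot be recovered later.

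The cost is a wording amendment, the memo, and a few more items at first contact for patients who would otherwise stop early. For most participants those items are already due as the next step; on the restricted withdrawal route they add to what is asked.

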7 DATA COLLECTION

7.1 Definition of time periods

Baseline is the day of randomisation until 23:59 that calendar day.

Study day 1 is the first calendar day after baseline from 00:00 to 23:59. All subsequent study days will follow accordingly.

Study day period is 00:00 to 23:59.

For the purpose of baseline data collection, all data will be extracted from the patient record and apply to the time leading up to randomisation (see details below)

7.2 Baseline

The following data will be collected:

Demographics: age, sex
Pre-existing health status:

- recalled SF-36 (PCS and MCS) 30 days prior to hospitalisation. Attempt to complete as close to the time of enrolment as possible. For patients lacking capacity at enrolment, this measure can be deferred until patients regain capacity
- Functional Co-morbidity Index (FCI)
- Clinical Frailty Index prior to the onset of the acute illness that resulted in this hospitalisation
- ICU Mobility Scale (IMS) at the time of randomisation
- Baseline health service utilisation questionnaire

Acute illness characteristics:

- ICU admission diagnosis
- APACHE II score
- o duration of mechanical ventilation
- o duration of renal replacement therapy (if required)
- SOFA score from the 24hrs period prior to the participant being ready for ICU discharge.

Blood sampling:

- 1. Blood required for cross matching: These samples should follow normal local procedures and are not considered research samples. Only send this sample if not available clinically and required for transfusion.
- 2. Hospital Laboratory (using local sampling volumes and processes): haemoglobin concentration; reticulocyte count; C Reactive Protein (CRP). These results should be collected for all trial participants. Existing results from samples taken <24hrs prior to randomisation can be used. It is acceptable to use the screening haemoglobin as the baseline haemoglobin if from <24 hours prior to randomisation. Use local procedures to 'add on' tests to appropriate existing clinical samples where possible (for example reticulocyte

count and CRP). If not available, the samples should be taken as part of clinical care but if not possible they should be taken as additional research samples.

Refer to section 5.1.3 for guidance on baseline Hb results and study procedures.

3. Blood sampling for mechanistic sub-study (research blood samples): For participants providing consent to participate in the mechanistic sub-study, up to 5mLs of blood should be taken, processed, and stored for: IL-6 concentration, ferritin concentration, transferrin saturation, soluble transferrin receptor concentration, hepcidin concentration, erythroferrone concentration and other inflammatory markers. (Every effort should be made to obtain this research blood sample, but it is not compulsory for inclusion. If the participant is reluctant or refuses to provide a blood sample for the mechanistic study they can still be recruited to the trial).

Refer to Sample Processing (Research Sample) document for processing instructions (see Appendix 3).

Where an appropriate clinical result is not available, all research blood samples including the mechanistic sub-study sample should be taken within **48 hours** of randomisation in the trial.

All research samples should be taken whenever possible **before any blood transfusion** has started, for example with the cross match sample or routine blood testing. In the event the transfusion is given prior to mechanistic blood sample collection, still collect the sample.

The research blood sampling including 5ml mechanistic sub-study will be up to a maximum of 20mls.

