5.1.3 Haemoglobin concentrations during screening and eligibility period

A patient can be screened as eligible for the trial based on any haemoglobin concentration during the eligibility period. If a haemoglobin concentration of 94g/L or less has been measured, and other inclusions/exclusions make the patient eligible, they can be approached for consent. Several scenarios based on the haemoglobin concentration may occur:

- a. The patient provides consent without any further haemoglobin measurement being undertaken for clinical or other reasons. In this situation the patient should be immediately randomised and managed according to the allocated group. There is no requirement to wait for the result of the baseline blood sample Hb measurement or any other Hb measurements before transfusing according to the protocol because the patient has demonstrated eligibility during the eligibility period.
- b. If the patient has been randomised, baseline blood samples have been taken, and the baseline or another Hb measurement becomes available before any transfusion has occurred, transfusion decisions should follow the protocol and group allocation using the most recent Hb concentration. The patient should remain in the trial once randomised and not be withdrawn if the Hb concentration is above 94 g/L on repeat Hb measurement. Transfusions should follow the protocol according to the most recent Hb measurement: for example if the Hb has increased on the baseline blood and is 94-99 g/L the patient should receive 1 unit of RBC if they are in the liberal group, with a target Hb of 100-120g/L. If they are in the restrictive group their Hb should simply be monitored, but they should not be withdrawn.
- c. If a patient is being screened and fulfils all eligibility and no exclusion criteria, *but has not yet provided consent* (for example lack of capacity or patient/family are still considering taking part) the following should guide participation:

- i. If a further Hb concentration is taken for clinical reasons *prior to consent* being obtained, and the result is >94 g/L, the patient is no longer eligible for the trial at that time.
- ii. If after (i) above, a further Hb concentration is taken for clinical or other reasons and is again ≤94 g/L the patient is again eligible if within the 7 days recruitment window. They can then be approached for consent.

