Moderation analyses of PCS SF-36 Score: We will conduct pre-specified moderation analyses on the primary endpoint. These moderation analyses will fit interaction terms for the baseline parameters and treatment group. There are 4 baseline potential moderators of interest – (a) Co-morbidity score (0-18; functional comorbidity index; a count of morbidities); (b) Recalled SF-36 score pre ICU admission; (c) ICU mobility scale (ordinal scale); and (d) Baseline level of systemic inflammation (CRP concentration; continuous measure ranging upwards from zero with normal values being <5mg/L). These analyses will explore how important these baseline parameters are in moderating how effective the intervention is for the main outcomes. We will first explore the nature of the potential interaction by fitting each baseline parameter as a continuous interaction with treatment, and if warranted, look at suitable categorisation (e.g. above vs. below the median) for ease of clinical interpretation.

Mediation analysis of PCS SF-36 score: We are also interested in understanding the mechanisms behind any treatment effect. To this end, in the main trial analysis we will conduct mediation analyses on the model described under "Principal analysis of PCS SF-36 score." The first mediation analysis will examine the role of haemoglobin concentration (anaemia severity) using blood measurements taken at baseline and 30 days post-randomisation, to determine whether this mediates the intervention's effect. Specifically, we want to assess whether the degree of anaemia correction at

30 days, according to group allocation, relates to the endpoint. The second mediation analysis will focus on systemic inflammation. Here, we will explore whether persistent inflammation mediates the impact of the number of blood transfusions on the endpoint. We will consider other potential mediators, and include these in the final SAP prior to locking the trial database.

We also plan to measure a range of biomarkers that may provide information about the mechanisms that the intervention influences the primary outcome, based on blood sampling at baseline and 30 days. These will include effects of the intervention on iron status, marrow erythrogenesis (red blood cell production), inflammation, and immune suppression. These exploratory analyses will be underpinned by a Directed Acyclic Graph (DAG) and pre-specified analysis plan.

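### Baseline research bloods may be drawn up to 48 hours after randomisation and after the first transfusion, mainly in the liberal arm, and the data listed cannot always show which came first

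*Protocol*

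**What the plan says.** **Sampling window.** Section 7.2 of the protocol states: "Where an appropriate clinical result is not available, all research blood samples including the mechanistic sub-study sample should be taken within" 48 hours of randomisation. On order relative to transfusion it says "All research samples should be taken whenever possible" before a transfusion has started, and suggests drawing them with the cross-match sample or routine bloods. For the mechanistic sample it continues: "In the event the transfusion is given prior to mechanistic blood sample collection, still collect the sample".

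**Separate route for the hospital laboratory tests.** For Hb, reticulocytes and CRP, section 7.2 says "Existing results from samples taken <24hrs prior to randomisation can be used", and for Hb in particular "It is acceptable to use the screening haemoglobin as the baseline haemoglobin if from <24 hours prior to randomisation". It encourages adding tests to existing clinical samples. If nothing usable exists, a new sample is taken in clinical care or, failing that, as a research sample.

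**Definition of baseline.** Section 7.1 says "Baseline is the day of randomisation until 23:59 that calendar day". It also says that baseline data describe the period before randomisation, and it points to the details that follow.

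**Transfusion.** The summary gives every intervention-arm participant one unit after randomisation. Section 6.1.2.4 asks for transfusion promptly and no later than 48 hours after the triggering Hb sample was taken. Usual care transfuses below 70 g/L unless the clinician modifies this.

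**Use of the values.** Section 9.2 names CRP as a moderator and as a candidate covariate. It runs the first mediation analysis on Hb "using blood measurements taken at baseline and 30 days post-randomisation", and it bases exploratory biomarker analyses on the same two time points.

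**The concern.** A baseline value should not be affected by the treatment under study. Here the sampling window and the first liberal-arm transfusion run over the same hours, and nothing in section 7.2 strictly requires the sample to come first. A late sample in usual care will usually still be untransfused. A late sample in the liberal arm often will not be. The resulting error is therefore related to arm.

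Three uses are at stake:

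- **Mechanistic analyses.** A change in iron, erythropoiesis or inflammation markers measured from a post-transfusion value no longer starts from an untreated reference.
- **Hb mediation.** A post-transfusion baseline Hb understates the correction of anaemia achieved by day 30 in the liberal arm. That correction is the quantity the analysis is meant to trace.
- **CRP moderation.** If transfusion alters CRP, an interaction with a post-treatment value is not moderation by a baseline characteristic.

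A later analysis rule can repair this only if the data show which event came first. Section 7.3 asks for date and time for Hb, but only date and number of units for transfusions.

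**Working it through.** **Step 1: do 7.1 and 7.2 agree?** Between 0 and 24 hours of the randomisation day remain after randomisation. Of the 48-hour window, 48 - 24 = 24 to 48 - 0 = 48 hours therefore fall after baseline has closed under section 7.1. Example: for randomisation at 15:00, baseline closes 9 hours later and 48 - 9 = 39 hours of permitted sampling lie outside it. In addition, every sample drawn after randomisation conflicts with the statement that baseline data describe the period before it.

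**Step 2: does the sampling window overlap the transfusion window?** The transfusion clock runs from the triggering Hb sample and the sampling clock from randomisation. If a pre-randomisation Hb taken 12 hours earlier (assumed) is the trigger, transfusion is due by 48 - 12 = 36 hours after randomisation, while sampling remains open until 48. The sampling window can outlast the transfusion window.

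**Step 3: which values are exposed?**

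| Measure | Pre-randomisation route | Exposed when |
|---|---|---|
| IL-6, ferritin, transferrin saturation, soluble transferrin receptor, hepcidin, erythroferrone | None stated for the stored research sample | The sample follows the first unit; collection is then expressly instructed |
| Hb, reticulocytes, CRP | Result from under 24 hours before randomisation | No such result exists and the replacement sample follows the first unit |

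**Step 4: can order be recovered?** With transfusions held by date only, a sample and a unit on the same date cannot be put in order. Appendix 3 asks sites to note oral iron and to match time of day between samples. It has no matching note for a transfusion given before the sample.

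**Step 5: how large could it be?** The plan gives no figure for this. Let f be the excess share of liberal-arm baseline Hb values drawn after a unit and d the rise per unit; both are assumed. The artificial between-arm shift is f x d. It is scaled below by the Hb SD of 9 g/L that section 1.1.3 gives for an earlier cohort.

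| f | d = 5 g/L | d = 10 g/L | d = 15 g/L |
|---|---|---|---|
| 10% | 0.5 (0.06 SD) | 1.0 (0.11 SD) | 1.5 (0.17 SD) |
| 25% | 1.25 (0.14 SD) | 2.5 (0.28 SD) | 3.75 (0.42 SD) |
| 50% | 2.5 (0.28 SD) | 5.0 (0.56 SD) | 7.5 (0.83 SD) |

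A change-from-baseline comparison of 30-day Hb would be understated by f x d. A baseline-adjusted one would be understated by slope x f x d. With an assumed slope of 0.3-0.6 this is 0.3 x 0.5 = 0.15 g/L up to 0.6 x 7.5 = 4.5 g/L.

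**Step 6: the primary comparison.** CRP is the only blood value among the candidate covariates. Let s be the shift in CRP after transfusion in SD units (assumed 0.1-0.5), r its correlation with PCS (assumed 0.1-0.3), and 12 the PCS SD from section 9.1. The bias is r x 12 x f x s. It runs from 0.1 x 12 x 0.1 x 0.1 = 0.01 to 0.3 x 12 x 0.5 x 0.5 = 0.9 points, against a target difference of 5. At f = 25% and s = 0.3 it is 0.09-0.27. The top of the range needs half the liberal arm to have CRP drawn after a unit.

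For the mechanistic markers the protocol offers nothing from which to size the shift.

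**The case against.** The strongest reply is that the protocol already makes pre-transfusion sampling the default and names a practical way to achieve it. On that view the line about collecting a late sample only stops sites from discarding it. That is a fair description of the intent, and it is why the contamination is possible rather than established. The preference still carries no consequence when it is missed.

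Two stronger readings are tempting, and the text supports neither:

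- A reader might infer that baseline Hb and CRP are contaminated as a matter of course. The express permission to sample after transfusion concerns the mechanistic sample alone. Hb and CRP have a pre-randomisation route and are exposed only when it fails.
- A reader might take "There is no requirement to wait for the result of the baseline blood sample Hb measurement" in section 5.1.3 to mean that transfusion goes ahead before the sample is drawn. It waives waiting for the result, not the draw. The next scenario in that section describes samples already taken when the result arrives.

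It can also be said that deciding which values count as baseline belongs in the analysis plan, which is not shown, and that the biomarker work is exploratory. Both are true. But the sampling window, the two definitions of baseline and the data items are set in the protocol, and an analysis rule cannot order events whose times were not captured. The case report form is not shown and may record more than section 7.3 lists. Section 7.1 does refer to later details, so section 7.2 could be read as an exception; the text does not say so.

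Finally, the qualifying Hb is a poor general substitute. It can be up to seven days old, and it was selected for being 94 g/L or lower, so a repeat value will tend to be higher. This stands and shapes the fix: the qualifying value should not displace a fresher pre-transfusion one.

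**Conclusion.** The concern holds in a limited form. Sections 7.1 and 7.2 contradict each other on when baseline ends. Section 7.2 permits baseline research samples after transfusion, and the transfusion schedule makes this more likely in the liberal arm. The mechanistic markers are the main exposure. Hb, reticulocytes and CRP follow only through the fallback route.

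The analyses at risk are the mechanistic ones, the Hb mediation and the CRP moderation. The primary PCS comparison is little exposed: baseline Hb is not among its listed covariates, CRP is only a candidate, and the protocol states no effect of transfusion on CRP. The sample size is not affected.

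The actual size is unknown, because the documents give neither the share of late samples nor the effect of one unit on any marker. The Hb range of 0.5-7.5 g/L and the CRP range of 0.01-0.9 PCS points show scale under assumed inputs and are not estimates. A reader might infer from them that the trial's main result is biased; they do not support that. The point is worth correcting because the error would follow treatment arm and the remedy is cheap.

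**What to change.** 1. Reconcile sections 7.1 and 7.2 so that one baseline window applies to blood samples.
2. Record the start time of the first post-randomisation transfusion and the time of every baseline sample, including the mechanistic one.
3. Define analysis baseline as the latest value within that window and before the first post-randomisation transfusion. The window is needed as a limit because some usual-care participants will never be transfused. For Hb, use the last pre-randomisation value where no later pre-transfusion value exists; eligibility guarantees that every participant has one.
4. Still collect later samples, but flag them and do not use them as baseline. Treat them as missing baseline in the moderation, mediation and mechanistic analyses, with a sensitivity analysis that includes them.
5. For Hb, add a sensitivity analysis that uses the last pre-randomisation value in both arms, so that differences in sample age between arms can be checked.

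No transfusion rule changes. The cost is one added time field for transfusion, confirmation that sample times are held, and a derived flag. For participants already enrolled, the time is needed only where sample and first unit share a date, and it would have to come from the medical record. Some late mechanistic samples, mostly in the liberal arm, are lost as baselines, so missingness will differ by arm; the sensitivity analysis in item 4 is there to show how much that matters.
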